After examining current literature, it is clear that vitamin D plays a crucial role in bone health and can affect the rate of skeletal-related injuries. Studies on military recruits provide promising data, but an important difference to note is musculoskeletal strength in recruits compared to conditioned athletes. Therefore, it is necessary to study the effects of vitamin D supplementation on bone health in athletes in order to help prevent stress fractures and related injuries. Our study would add to the current deficit in this area of research and would allow athletes and teams to adjust diets and training plans accordingly. The principal investigator has observed an increase rate in stress fractures in those athletes who participate in the following sports: basketball, soccer, track/field, and cross country for both male and females athletes. The overall aim is to demonstrate the evidence of stress fracture prevention in order to keep athletes performing at their highest abilities.

Objectives/Research Aims

Objectives

The main objective of this study is to find a correlation between vitamin D deficiency and stress fracture occurrences in athletes who participate in high-risk activities. These high-risk athletes undergo elevated bone turnover, which requires adequate levels of vitamin D in order to support bone health. It is hypothesized that providing supplemental treatment to athletes showing lower than normal serum vitamin D levels will decrease the occurrence of stress fractures. By recording the dates and specific occurrences of fractures, it may be possible to correlate injury rates with seasons, providing more supportive data to pre-existing literature.

This area of research is lacking in the quantity of prospective studies. Previous studies primarily focus on adolescent, elder, or military recruit populations. While literature has shown that vitamin D plays an important role in bone health, there are no previous studies that directly examine vitamin D deficiency and supplemental treatment in conditioned collegiate athlete populations. This study will add to the existing knowledge and will provide a more specific analysis for athletes.

Specific Aims

1. To compare the proportions of student athletes experiencing stress fractures during the 2015-16 academic year with the five previous years.

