of the extreme stresses involved when jumping. Combining all four sports as a single cohort would provide an adequate number of athletes to form a test group. Each sport's season occurs at different times of the year, and indoor sports like basketball and track may have athletes with less sun exposure. This will allow a comparison of occurrences across different sports, not just between treatment and control groups. Depending on the number of individuals meeting criteria for the study, it may be necessary to extend the timeframe to multiple seasons. The initial phase of the study will include a retrospective analysis of data from deficient athletes in these sports from past seasons that have not received any supplemental treatment. This will be used to find the percentage of stress fracture incidences occurring during those seasons.

The staff directly working on the study will consist of a licensed orthopedic surgeon, a doctor of athletic training and nutrition, a physician in occupational medicine, a research assistant, and a master's student. During each individual sport's season, other athletic trainers, physicians, and coaching staff may offer assistance as well. Every individual engaged with the study will be familiar with the basics of the topic and protocol as a minimum. The physicians will provide most of the expertise and insight when providing care for the athletes. Should any unexpected consequences arise, the staff and athletes will have direct access to both orthopedic and athletic training facilities as well as the linked hospital and clinics. The staff is in constant communication and will have regular meetings in order to stay current on the progress of the study.

Prior Approvals

Each individual sports team member, along with the coaching staff, team physicians, and athletic trainers, will be informed of the study. Approval will be required from the teams listed, as well as from the University of South Carolina Orthopedic Clinic.

Study Design

a) Recruitment Methods

Potential subjects will be screened from men's and women's track and field, soccer, and basketball teams, and women's cross-country. Individual players of each described team will be informed of the study during their pre-season physical. It is hoped that every player on the specified teams will be able to enroll in the study, whether they are vitamin D deficient or not.

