Any subject that has consented and meets inclusion/exclusion criteria will be tested for serum vitamin D levels, and those individuals showing deficiency will be provided supplemental treatment in order to raise vitamin D levels to normal ranges. Individuals who do not show deficiency levels will be included in the study, but will not receive any treatment. These subjects will be added to an additional control group. There will be no payment for enrollment in the study.

b) Inclusion/Exclusion Criteria

Each individual who has given consent will have blood work tested. Should serum vitamin D levels be lower than 30 ng/mL, they will be included in the treatment group. Subjects with normal ranges will be included in the prospective control group. Both male and female athletes will be eligible to enroll. Any individual who currently has a stress fracture or is in the stage of recovering from a lower extremity musculoskeletal injury will be excluded from the study. Questionnaires will be provided in order to gather an understanding of diet, exercise regimen, and related lifestyle questions. Specifically, there will be a question regarding current vitamin D or other multivitamin supplement currently being taken, what the dosage is, and how often it is taken. Female athletes will be provided a separate questionnaire in regards to individual dietary habits and menstrual cycle.

c) Local Number of Subjects

The number of subjects in the study will be based on the number of individuals meeting the inclusion/exclusion criteria and provide written consent. They will be drawn from men's basketball, soccer, and track/field, and women's basketball, soccer, track/field, and cross-country. There will be no cutoff to the number of individuals accepted. Tentatively, there will be roughly 200 athletes enrolled in the study.

d) Study-Wide Number of Subjects

The number of subjects in the prospective portion of the study will be the number of qualified enrollees. This number may change, depending on the length of the study. Should it be necessary to extend the timeline, the study will enroll new subjects for the second season, but will still include them in the test group.

e) Study Timelines

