Each enrolled subject will be monitored from the time of their pre-season physical to the conclusion of activities for their particular sport. The pre-season physicals will occur in August 2015, prior to the start of the school year. Subjects will be enrolled in the study even if the sports season has not begun. In the event of a study extension, any athlete partaking in a subsequent season will be asked to remain in the study as long as inclusion/exclusion criteria is met. The estimated date of completion is July of 2016, but may be extended if the data is inadequate for completion of the study.

Following the initial examination, all subjects will have serum 25(OH) vitamin D levels tested again in January. Subjects with deficient levels receiving treatment will undergo a follow-up examination 8 weeks from the initial treatment. This will help determine if subjects are responding to the treatment.

f) Study Endpoints

The primary endpoint of this study will be marked as when enough data has been collected to show a correlation between supplemental treatment and stress fracture occurrence, whether it is positive or negative. Tentatively, data collection for the study will stop at the conclusion of the last sports season. It may be necessary to extend the study for an additional school year if there are not enough data points to show a true correlation.

Supplemental treatment of 25(OH) vitamin D3 may have several adverse effects, including hypervitaminosis D and hypercalcemia. Should any subject show symptoms of these issues, they may be removed from the study.

g) Procedures Involved

Prospective: Subjects will be enrolled starting in August 2015, following the pre-season physical. It is possible many subjects, including returning athletes, may have taken summer physicals, and those subjects will be recruited and tested at a date upon return to school. Subjects should be tested prior to the start of individual seasons, although some overlap may occur. A flowchart is attached.

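### The primary endpoint and a possible extra year are tied to the data showing a correlation; this leaves room for result-driven extension, and Aim 1 does not say how an extension season is analysed

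*Combined protocol and SAP*

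**What the plan says.** Section f) Study Endpoints does not name an outcome variable. It places the primary endpoint at the moment "when enough data has been collected to show a correlation between supplemental treatment and stress fracture occurrence, whether it is positive or negative". Data collection is tentatively to end with the last sports season, but it may be necessary to "extend the study for an additional school year if there are not enough data points to show a true correlation".

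Two other passages also allow an extension. Resources Available says: "Depending on the number of individuals meeting criteria for the study, it may be necessary to extend the timeframe to multiple seasons". Section e) Study Timelines gives July 2016 as the estimated completion date, which "may be extended if the data is inadequate for completion of the study". None of the three gives a minimum number, a decision date or a decision-maker.

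For an extension, section d) Study-Wide Number of Subjects says "the study will enroll new subjects for the second season, but will still include them in the test group", and section e) says "any athlete partaking in a subsequent season will be asked to remain in the study". On follow-up, section e) says: "Each enrolled subject will be monitored from the time of their pre-season physical to the conclusion of activities for their particular sport".

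The comparison itself is fixed to one year. Aim 1 reads "To compare the proportions of student athletes experiencing stress fractures during the 2015-16 academic year with the five previous years". Item 1 of section i) Statistical Analysis uses a large-sample test of two independent proportions, with a group variable that sets 2015-16 against the previous four years. No second prospective season, interim test or alpha adjustment is mentioned.

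**The concern.** An endpoint should say what is measured in each athlete. Here it is worded as the point at which a relationship has become visible, and the extra year is offered if it has not. Read literally, that makes the length of the study depend on the result. If Aim 1 were tested after 2015-16, found non-significant, and tested again at 0.05 with another year's athletes, the overall false-positive rate would exceed 5%. The phrase covering both directions makes the rule neutral as to sign, but does not stop it depending on the result.

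The second gap is what Aim 1 becomes after an extension. The protocol expects both newcomers and returners, but no passage says how a second season enters the test or over what window a two-season athlete is counted. Counting returners over two seasons against controls counted per season would give the prospective group roughly twice the exposure per returner, which biases Aim 1 against the treatment.

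**Working it through.** **1. The plan's own power figure.** Inputs from the table in section i): N1 = 200, N2 = 800, P1 = 0.04, P2 = 0.10, two-sided 0.05, pooled Z test.

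- Pooled proportion = (200×0.04 + 800×0.10)/1000 = 0.088.
- SE under H0 = √[0.088×0.912×(1/200 + 1/800)] = 0.02240.
- SE under H1 = √[0.04×0.96/200 + 0.10×0.90/800] = 0.01745.
- Power = Φ[(0.06 − 1.96×0.02240)/0.01745] = Φ(0.923) = 0.822.

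This matches the stated 0.8220. It is correct for one fixed analysis of 200 versus 800 and does not cover an extension.

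**2. Two unadjusted looks.** Suppose Aim 1 is tested at 0.05 with 200 versus 800 and, if not significant, again with n₂ distinct prospective athletes against the same 800. Under no effect the two Z statistics have correlation ρ = √[(1/n₂ + 1/800)/(1/200 + 1/800)], and the overall error is P(max|Z| > 1.96). The documents give no extension size, so n₂ is assumed; 400 means a second season of 200 entirely new athletes and is close to an upper case.

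| n₂ | ρ | Type I error |
|---|---|---|
| 220 | 0.963 | 6.3% |
| 250 | 0.917 | 6.9% |
| 300 | 0.856 | 7.4% |
| 400 | 0.775 | 8.0% |

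Binomial simulation at a 10% rate agrees (6.36%, 6.85%, 7.41%, 7.94%). The nominal 95% interval then covers 94.2% down to 93.0%, against 94.6% to 94.8% for one fixed look. If the study were extended only when the first p-value lay between 0.05 and 0.10, 0.20, 0.30 or 0.50, the error at n₂ = 400 would be about 5.9%, 6.9%, 7.3% or 7.7%.

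**3. Enrolment-only trigger, one test.** With season-one enrolment assumed uniform on 120 to 239, topped up to 200 if short, and a single test, the error is 5.0%.

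**4. The counting window.** Assume 200 athletes each season, independent seasons, and 800 controls counted per season (4×200). With 180, 150 or 100 returners there are 220, 250 or 300 distinct athletes. Two-season risk is 1 − (1 − p)²: 0.190 at p = 0.10 and 0.0784 at p = 0.04.

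If returners are counted as ever-fractured over both seasons and there is no treatment effect, the expected prospective proportion with 180 returners is (180×0.190 + 40×0.10)/220 = 17.4%, against 10% in controls. With 150 or 100 returners it is 15.4% or 13.0%. Exact enumeration of the pooled Z test gives:

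| Returners | Power, 4% vs 10% per year, two-season count | Power, each athlete once over one year | Wrongly shows more fractures when there is no effect (two-season count) |
|---|---|---|---|
| 180 | 24% | 86% | 83% |
| 150 | 43% | 90% | 64% |
| 100 | 73% | 94% | 30% |

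**5. Same unit in both groups.** Counting athlete-seasons gives 400 versus 800. The pooled proportion is 0.08, the SEs are 0.01661 and 0.01444, and power = Φ[(0.06 − 1.96×0.01661)/0.01444] = Φ(1.900) = 0.971. Simulated type I error is 4.9% to 5.0% with independent seasons. With an assumed within-athlete correlation of 0.1 to 0.2 and no variance adjustment it is 5.4% to 6.4%.

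**The case against.** The best defence is that the triggers are phrased as amounts: data points in section f), individuals meeting criteria in Resources Available. With the neutral wording on direction and only one test described in section i), this favours the quantity reading, under which nothing is inflated. That stands. A reader might infer that the protocol plans repeated testing until significance; the documents schedule no second test and do not support that.

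A reader might also take the second table in the working as what an extension would produce. It is not. Those figures pair controls counted per season with returners counted once over two years, a mixture no passage prescribes. Aim 1 is per academic year, Setting refers to an incidence percentage from previous seasons, and follow-up in section e) runs to the end of the sport's activities; all point to a per-season or per-year count. With matched athlete-seasons the problem disappears. The figures also rest on independent seasons: at a within-athlete correlation of 0.2 the 83% falls to 67% and the 24% power rises to 35%. What stands is that the window after an extension is never stated, so the mixture has to be ruled out.

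Finally, a fracture-count trigger is a plausible meaning of data points. In this design it would not be neutral: the historical count is fixed and obtained in the study's initial phase, so the number of fractures among prospective athletes is in effect the result. That is why enrolment is the safer basis.

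**Conclusion.** The concern holds in a limited form and should be fixed. Section f) does not name an outcome, and its wording leaves open an extension that depends on the result. If used that way with unadjusted tests, type I error would be about 6.3% to 8.0% rather than 5%, for an assumed 220 to 400 distinct prospective athletes. Under the quantity reading with one test it stays at 5%. Separately, the Aim 1 analysis after an extension is unspecified. Counting over unequal windows would bias it against the treatment, but that is a risk to exclude, not what the plan prescribes. Apart from the endpoint wording, all of this matters only if the study is extended, which the protocol presents as a possibility.

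**What to change.** 1. In section f), state the primary endpoint as the proportion of athletes with at least one physician-confirmed lower-extremity stress fracture (as defined in section g) Procedures Involved) per academic year.
2. Delete both conditions about showing a correlation. Replace the three triggers with one based only on the number enrolled, for example fewer than the 200 in the power table, decided before any Aim 1 comparison.
3. Run one final Aim 1 test at 0.05, and reword Aim 1 and its group variable to include any extension season.
4. Count prospective and historical athletes in the same unit and window: either athlete-seasons in both groups with standard errors clustered by athlete, or each athlete once over one academic year in both groups. No passage states the per-athlete window for the historical records, so it must be written down.

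**Cost.** Wording changes and, with athlete-seasons, a cluster-robust variance. Counting each athlete once gives up some power after an extension: about 86% to 94% against 97% for 4% versus 10%, with 200 athletes per season, 100 to 180 returners and 800 controls, all assumed. An enrolment trigger guards against a shortfall (by the plan's own formula, 70% power at 150 athletes and 59% at 120). A threshold of 200 enrolled does not by itself secure 80%, however. Section m) Withdrawal of Subjects leaves withdrawn athletes out of the final analysis, and power is 78% with 180 analysed and 73% with 160. The sponsor may want to set the threshold with that in mind.

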Other than normal activities required for each sport, the main risk to each subject primarily involves taking blood samples. Although sampling is routine, there will still be risks of bleeding, bruising, dizziness, and possible infections. Allowing only trained individuals to take blood samples will minimize these risks. Any injury that occurs during a sports event or training activity will be handled accordingly by one of the physicians or athletic trainers on site. All injuries, regardless of nature, will be recorded per subject.

Blood samples will be tested for 25(OH) vitamin D levels using the order (Vitamin D 25-OH, Calcifediol Request). The data will be kept for each subject, day of recording, and level on an Excel spreadsheet. Any stress fracture reported will be listed on the same spreadsheet, along with the date of occurrence and severity, per subject.

Each team's athletic training staff will administer one vitamin D capsule to each team member once a week before a scheduled meeting or practice. This will help ensure every athlete takes the proper dosage, no dosages are skipped, and every week is accounted for. Athletes may still have decreased levels after the first course, and a second round of 8-week treatment will be administered. Should the second round of treatment fail to elevate vitamin D levels, the January test will confirm and treatment will continue. As many students leave to visit family during break, it will be rather difficult to monitor every athlete's levels during this timeframe.

Retrospective: The retrospective portion of the study will involve review of athletes of the same sports teams and inclusion/exclusion criteria from seasons up to four years ago. Review of previous athlete information will be drawn from electronic records kept by the athletic training staff, both electronic and hand-written records kept by the orthopedic staff, and any lab records retained at Palmetto Health. The information that will be obtained will include athlete demographics, their respective sports, stress fracture occurrences, and vitamin D levels if this was noted. The time period for the retrospective chart review will be from January 2010 through August 2015. The rate of stress fracture occurrence will be compared to the prospective treatment phase. It is important to note that individuals in the retrospective analysis will not have personal information reported, as the main purpose is to determine a baseline stress fracture rate.

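### Late enrolment with a current-injury exclusion drops early 2015-16 fractures from Aim 1, and no matching index date is set for the historical seasons

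*Combined protocol and SAP*

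**What the plan says.** Section e) Study Timelines sets the start of follow-up: "Each enrolled subject will be monitored from the time of their pre-season physical to the conclusion of activities for their particular sport". That covers enrolled athletes only.

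Section g) Procedures Involved (Prospective) separates enrolment from the physical. It opens with "Subjects will be enrolled starting in August 2015, following the pre-season physical", then notes that many athletes may have had their physical in the summer, and "those subjects will be recruited and tested at a date upon return to school". It gives no latest date. The next sentence reads "Subjects should be tested prior to the start of individual seasons, although some overlap may occur".

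Eligibility comes before testing. Section a) Recruitment Methods says "Any subject that has consented and meets inclusion/exclusion criteria will be tested for serum vitamin D levels", and section b) Inclusion/Exclusion Criteria says "Any individual who currently has a stress fracture or is in the stage of recovering from a lower extremity musculoskeletal injury will be excluded".

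For the comparison years, section g) (Retrospective) plans a "review of athletes of the same sports teams and inclusion/exclusion criteria from seasons up to four years ago", using charts from January 2010 through August 2015. It does not say on what date in each past season the criteria are to be applied.

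Section i) Statistical Analysis tests Aim 1 as a difference between two independent proportions. Sport and gender enter only as covariates in an exploratory logistic model.

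**The concern.** Take two teammates whose season has begun before they are approached. One develops a stress fracture in the first weeks. When approached, that athlete is ineligible and counts neither as a case nor as a member of the cohort. The other stays healthy, enrols and is counted. The plan nowhere says that fractures before enrolment are logged or added back.

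In a past season nobody was approached, so there is no natural moment at which to ask whether an athlete is currently injured. Unless a reviewer invents such a date, an early-season fracture found in the chart is likely to be counted. The same criteria without the same time zero do not give the same screening.

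This is selection at entry. At stake is the main comparison: the 2015-16 proportion could look lower than history for a reason that has nothing to do with vitamin D. The test has no adjustment for this, and the sport and gender covariates cannot restore athletes who were never enrolled.

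**Working it through.** **Inputs from the plan** (section i), Sample Size Justification): 200 athletes in 2015-16, 800 historical, control proportion 10%, two-sided alpha 0.05, pooled-variance Z test.

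**Inputs that are assumptions:** *s*, the share of 2015-16 athletes tested after team activity starts, and *f*, the share of those athletes' fractures that come before their test. The documents give neither.

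**Step 1: reproduce the plan's figure.** For 4% versus 10%:
- pooled proportion = (200×0.04 + 800×0.10)/1000 = 0.088
- standard error under no difference = √[0.088×0.912×(1/200 + 1/800)] = 0.02240
- standard error under the alternative = √[0.04×0.96/200 + 0.10×0.90/800] = 0.01745
- power = Φ[(0.06 − 1.96×0.02240)/0.01745] = Φ(0.923) = 0.822

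The plan states 0.8220. The other rows of its table also reproduce to within 0.002, so the power table is not in question.

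**Step 2: the apparent 2015-16 rate with no true effect.** Removing early cases from numerator and denominator of the late-tested athletes gives

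rate = (1 − s)×0.10 + s×0.10(1 − f)/(1 − 0.10f).

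For example, s = 0.5 and f = 0.15 gives 0.05 + 0.5×0.085/0.985 = 0.0931. The expected number of fractures screened out, of about 20 in 200, is 20×s×f.

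**Step 3: the chance of a falsely significant reduction.** I enumerated all outcomes of two binomials (200 at the apparent rate, 800 at 10%) and summed the probability that the pooled Z statistic falls below −1.96.

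| s | f | fractures screened out | apparent rate | chance of false reduction |
|---|---|---|---|---|
| 0 | 0 | 0 | 10.0% | 2.1% |
| 0.25 | 0.05 | 0.25 | 9.9% | 2.4% |
| 0.50 | 0.10 | 1.0 | 9.5% | 3.3% |
| 0.50 | 0.15 | 1.5 | 9.3% | 4.0% |
| 0.50 | 0.30 | 3.0 | 8.6% | 7.4% |

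These rows assume that the historical count loses no early fractures.

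**Step 4: equal screening in both periods.** Putting the same reduced rate in both groups returns the chance to 2.1% at s = 0.5, f = 0.30, and to 2.0% at s = 1, f = 0.30. The distortion therefore comes from unequal screening between periods, not from the exclusion itself.

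**Limits.** The formula removes every fracture before the test, while section b) excludes only current or recovering injury, so it slightly overstates the loss. Athletes excluded for other lower extremity injuries are not modelled.

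**The case against.** The strongest reply is that the retrospective review is to use the same inclusion and exclusion criteria, so both periods are meant to be screened alike. As a statement of intent this stands, and Step 4 shows that equal screening would remove the problem. It is not sufficient as written, because an exclusion for a current injury needs a date and none is given for past seasons.

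Second, the schedule limits how much can be lost. Physicals are in August, testing before the season is the stated rule, and seasons fall at different times of year. Two possible 8-week courses before a January test (16 weeks) imply baseline testing by about mid-September. That argues for the smaller rows of the table. But the plan itself says that many athletes may be recruited late, and it sets no limit.

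Third, a fracture between a summer physical and the return to school lies largely outside the academic year, and excluding it is ordinary practice. Agreed: only the interval from the start of team activity to enrolment matters.

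A reader might infer more than the documents support:
- **That the false-reduction chance is about 21%.** This needs every athlete to be tested late with 30% of fractures already past. Section g) makes late testing an exception to the rule, so it does not support that case.
- **That this is immortal-time bias.** Section i) compares simple proportions, and no person-time is credited to anyone.
- **That Aims 2 and 4 are biased in the same way.** Aim 2 groups athletes by baseline level and Aim 4 concerns later fractures. Excluding injuries present at the test is right for both.

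**Conclusion.** The concern holds for Aim 1 in a limited form. Late enrolment and the current-injury exclusion together remove early 2015-16 fractures, while the historical seasons have no index date at which an equivalent removal would occur. The lost cases can only lower the 2015-16 proportion, which favours the study hypothesis.

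The size cannot be fixed from the documents. Under the shares assumed above, the added risk of a false reduction runs from negligible (2.4% against 2.1%) to about three and a half times the starting value (7.4%). It would be nil if the chart review happened to screen equally. Because the plan neither limits late testing nor asks for a report of its extent, a reader of the results could not tell which case applied. The correction is worth making before analysis, but the design does not fail on this point.

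**What to change.** For Aim 1, define one index date per sport and season, for example the first organised practice, and use it in 2015-16 and in every historical season. An index date for 2015-16 alone would leave the comparison undefined on the other side.

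- In section b) and in the retrospective part of section g), apply the current-injury exclusion as of that date in both periods.
- In section i), count fractures from that date onward. In 2015-16, include those of otherwise eligible, consenting athletes who fracture before the blood test.
- Keep Aims 2 and 4 starting at the blood test.
- Report how many athletes were tested after the index date and how many were excluded for a current injury. Section g) already provides for recording the day of each blood level and the date of each fracture.

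**Cost.** Protocol and analysis wording, consent and outcome data from a few athletes who are already injured, and an index date to assign in the chart review. The 2015-16 proportion will be slightly higher and will include some fractures before any supplementation. That fits Aim 1 as worded, a comparison of academic years. It departs from the Sample Size Justification, which describes athletes with normal levels at baseline or after treatment, so the choice should be stated. No treatment changes.
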